Sacroiliitis (inflammation of the sacroiliac joints) is the radiological hallmark of axSpA, but other spinal lesions include spondylitis (inflammation of the vertebral bodies) spondylodiscitis (inflammation of the vertebral discs), enthesitis (inflammation of the spinal ligament insertion points) and the formation of syndesmophytes in chronic disease. Historically, axSpA has been diagnosed using plain radiographs of the sacroiliac joints to assess for sacroiliitis according to the 1984 modified New York criteria for AS [15]. However, over the last 20 to 30 years, cross-sectional imaging with computed tomography (CT) and magnetic resonance imaging (MRI) has become increasingly utilised. CT scans can better detect chronic bony changes in axSpA, including erosions, sclerosis and ankylosis, compared with radiographs [16-19]. However unlike MRI, they are unable to identify acute inflammatory changes related to bone marrow oedema or chronic changes related to fatty atrophy and MRI is much more effective at detecting early signs of axSpA [16, 20-22]. CT scans also pose higher ionising radiation exposure. MRI does not pose an ionising radiation risk and has therefore been recommended for the assessment of SpA in the 2009 ASAS guidelines [16]. Regarding PsA, this can be diagnosed using the CASPAR criteria [23].

The acute inflammatory changes of axSpA are best seen on MRI using dedicated fluid sensitive sequences such as a fat saturated T2-weighted sequence or a short tau inversion recovery (STIR) sequence. The typical active inflammatory lesions of the sacroiliac joint on MRI include bone marrow oedema, capsulitis, enthesitis and synovitis, and the chronic lesions include sclerosis, erosions and ankylosis [24]. The typical axSpA MRI spinal lesions include spondylitis, spondylodiscitis, enthesitis and syndesmophytes [16].

MRE imaging has been shown to be a useful tool in the diagnosis and assessment of potential complications for patients with CD [25, 26]. The majority of CD patients will have been reviewed by secondary care specialists in gastroenterology, and most will have had cross-sectional imaging in the form of MRE imaging to assess the extent of their CD. These scans also capture the axial (spine and

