4.3.3 Axial MRI Scan

Non-contrast MRI imaging of the whole spine and sacroiliac joints, using a dedicated protocol including T1 weighted and fluid sensitive sequences, will be performed in both the cases and controls. Images will be reviewed by two independent expert musculoskeletal radiologists ([name] and a colleague musculoskeletal radiologist) and any discrepancies will be decided by consensus agreement. Since MRI review by a second radiologist is not standard of care, it is funded by the research grant for the clinically indicated axial MRI scans. The MRI review by both of the radiologists for the axial MRI scans performed for research purposes is funded by the research grant.

These will be assessed and scored using the spondyloarthritis research consortium of Canada (SPARCC) MRI index criteria which is a validated scoring system for the assessment of spinal and sacroiliac joint inflammation on MRI [43, 44]. To calculate the SPARCC MRI index criteria score for the spine, the six most abnormal discvertebral levels on the STIR sequence are used. At each of the 6 levels, 3 consecutive slices are included and each slice is divided into four quadrants with each quadrant being scored as normal (score 0) or increased signal (score 1). In addition, each slice is scored for intensity and depth of inflammation to give a total possible score of 108 (see Appendix 8). To calculate the SPARCC MRI index criteria score for the sacroiliac joints, six coronal slices of the

sacroiliac joints on the STIR sequence are chosen and each slice is divided into four quadrants. Each quadrant is then scored as normal (score 0) or increased signal (score 1). In addition, each slice is scored for intensity and depth of inflammation to give a total possible score of 72 (see Appendix 9). The SPARCC MRI index criteria has been validated and reported to be the most reliable MRI inflammation scoring system in a number of studies due to its sensitivity to changes and high inter-reader reliability [45-47]. The dedicated MRI scans will also be scored using the specifically designed scoring system as follows:

- i) Joint margins and contour (score range 0 – 2; 0=normal, 1=mildly abnormal, 2=severely abnormal)
- ii) Juxta-articular bone marrow signal (0 – 3; 0=normal, 1=mild, 2=moderate, 3=severe)

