The SPARCC MRI index criteria score will then be used to determine the validity of our specifically designed scoring system for the dedicated axial MRI scans. The scores of the dedicated MRI scans will then be compared to the MRE scores for each patient to determine the validity of using MRE as a screening tool for axSpA in patients with CD. The sensitivity, specificity and area under the ROC curve of using MRE as a screening tool will also be determined.

If an unexpected finding is identified, such as a fracture or potential malignancy, then the gastroenterology team will be informed and appropriate onward referrals and communication (in-person or telephone, as deemed clinically appropriate) to the patient will be made.

5. Study subject selection

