5. Bone marrow signal in the centre of each vertebra constitutes the reference normal signal. If the entire vertebra is abnormal, closest normal level is used for reference. Do not score disc lesions.
6. Each discovertebral level is divided into four quadrants: 1 upper anterior endplate, 2 upper posterior endplate, 3 lower anterior endplate, 4 lower posterior endplate. The presence of increased signal in each quadrant is recorded for each of the 3 sagittal slices. Maximum score is 12 per discovertebral level. Maximum score for 6 levels = 72
7. A score for “intense” may be assigned to each level on each slice. High signal from cerebrospinal fluid acts as a reference for assigning an “intense” reading score to a bone lesion. A score of 1 is assigned if “intense” signal is seen in any quadrant on a single slice. Therefore maximum score per slice is 1, per level is 3 and for 6 levels = 18.
8. A score for “deep” may be assigned to each level on each slice. A lesion is graded as “deep” if there is homogeneous and unequivocal increase in signal extending over a depth of at least 1 cm from the surface of the endplate. A score of 1 is assigned if “deep” signal is seen in any quadrant on a single slice. Therefore maximum score per slice is 1, per level is 3 and for 6 levels = 18.
9. Pre- and post-treatment MR images are scored together with observer blinded to time sequence.

Total maximum score is 108:

Presence of “bone marrow oedema” = 72

Presence of “intense oedema” = 18

Presence of “deep oedema” = 18

Appendix 9: The spondyloarthritis research consortium of Canada (SPARCC): Magnetic Resonance Imaging index for scoring inflammation in the sacroiliac joints[44].

SCORING METHODOLOGY

1. All scores are dichotomous – present or absent, 1 or 0.
2. Only 6 coronal slices are assessed. Slices 4-9 are usually selected as those representing the largest proportion of the synovial compartment of the SI joints. Images scored at a second time point are selected to correspond as closely as possible to the first time point – normally 4-9, 3-8 or 5-10.
3. Only abnormalities on the STIR sequence are scored. T1 SE images are included for anatomical reference.
4. Score all lesions within the iliac bone. Within the sacrum, score lesions medially as far as the lateral border of the sacral foramina.
5. Sacral inter-foraminal bone marrow signal is used as the reference for normal to determine a threshold for increased signal in periarticular bone.

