6. Each SI joint is divided into four quadrants: 1 upper iliac, 2 lower iliac, 3 upper sacrum, 4 lower sacrum. The presence of increased signal in each quadrant is recorded. Maximum score for two SI joints in each coronal slice is 8. Maximum score for 6 coronal slices = 48.
7. A score for “intense” may be assigned to each SI joint on each slice. High signal from slow flowing venous blood within presacral veins acts as a reference for assigning an “intense” reading score to a bone lesion. A score of 1 is assigned if “intense” signal is seen in any quadrant of an SI joint on a single slice. Maximum score per slice is therefore 2, and for 6 slices = 12.
8. A score for “deep” may be assigned to each SI joint on each slice. A lesion is graded as “deep” if there is homogeneous and unequivocal increase in signal extending over a depth of at least 1 cm from the articular surface. A score of 1 is assigned if “deep” signal is seen in any quadrant of an SI joint on a single slice. Maximum score per slice is therefore 2, and for 6 slices = 12.
9. Pre- and post-treatment MR images are scored together with observer blinded to time sequence.

Total maximum score is 72:

Presence of “bone marrow edema” = 48

Presence of “intense edema” = 12

Presence of “deep edema” = 12

14. References

1. Stolwijk, C., et al., *Epidemiology of spondyloarthritis*. *Rheum Dis Clin North Am*, 2012. **38**(3): p. 441-76.
2. Sheehan, N.J., *The ramifications of HLA-B27*. *J R Soc Med*, 2004. **97**(1): p. 10-4.
3. Jadon, D.R., et al., *Axial Disease in Psoriatic Arthritis study: defining the clinical and radiographic phenotype of psoriatic spondyloarthritis*. *Ann Rheum Dis*, 2017. **76**(4): p. 701-707.
4. Ozgul, A., et al., *Effect of ankylosing spondylitis on health-related quality of life and different aspects of social life in young patients*. *Clin Rheumatol*, 2006. **25**(2): p. 168-74.
5. Ward, M.M., et al., *Impact of ankylosing spondylitis on work and family life: comparisons with the US population*. *Arthritis Rheum*, 2008. **59**(4): p. 497-503.
6. Healey, E.L., et al., *Ankylosing spondylitis and its impact on sexual relationships*. *Rheumatology (Oxford)*, 2009. **48**(11): p. 1378-81.
7. Tillett, W., C. de-Vries, and N.J. McHugh, *Work disability in psoriatic arthritis: a systematic review*. *Rheumatology (Oxford)*, 2012. **51**(2): p. 275-83.

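### SPARCC scores only STIR abnormalities, so it cannot validate the joint-margin item of the new sacroiliac score

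*Combined protocol and SAP*

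**What the plan says.** Section 4.2.1 introduces a scoring system built for this study to pick up sacroiliitis on both MRE and dedicated MRI, and says that it has not yet been used in practice. It has two sections: "Joint margins and contour" (0-2) and juxta-articular marrow signal (0-3). The grades are labelled from normal to severe but not defined further.

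Section 4.3.3 applies this score to the dedicated MRI alongside SPARCC, which it calls a "validated scoring system for the assessment of spinal and sacroiliac joint inflammation on MRI". It then sets the validation rule: "The SPARCC MRI index criteria score will then be used to determine the validity of our specifically designed scoring system". The next step compares the dedicated MRI scores with the MRE scores to judge MRE as a screening tool.

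Appendices 8 (spine) and 9 (sacroiliac joints) share one rule: "Only abnormalities on the STIR sequence are scored. T1 SE images are included for anatomical reference". The SPARCC points count the presence, intensity and depth of oedema.

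Section 2.1 separates active from chronic sacroiliac disease on MRI: "the chronic lesions include sclerosis, erosions and ankylosis". It also says that MRI can show chronic fatty change.

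Section 8.2 plans regression of MRE scores against dedicated MRI scores. It names no statistic or threshold for the new score against SPARCC.

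**The concern.** A criterion can validate only what it measures. SPARCC measures inflammation, whereas the margin item, going by its name and by the chronic lesions listed in section 2.1, grades structural change. The rule in 4.3.3 draws no distinction between the two items.

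The result could mislead in two directions. Scans with old structural disease and no current oedema would be recorded as disagreement although both scores were read correctly. Conversely, good overall agreement carried by the marrow item could be taken to cover a margin item that was never tested. Such scans are plausible, because section 1.5 admits subjects with known SpA, who may have longstanding disease.

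This matters because the score is new and SPARCC is the only established MRI score against which it is to be checked. The later MRE comparison relies on the same score.

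**Working it through.** **1. Reproduce the plan's SPARCC maxima.**
- Sacroiliac (Appendix 9): 6 slices × 2 joints × 4 quadrants = 48 for oedema; 6 × 2 = 12 for intense; 6 × 2 = 12 for deep. Sum 48 + 12 + 12 = 72, which matches "Total maximum score is 72".
- Spine (Appendix 8): 6 levels × 3 slices × 4 quadrants = 72; 6 × 3 = 18 for intense; 6 × 3 = 18 for deep. Sum 72 + 18 + 18 = 108, which matches "Total maximum score is 108".

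The STIR components account for the whole of each total, so 0 of 72 and 0 of 108 points can come from joint margins.

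**2. Set the items against the criterion.**

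| Item of new score | Range | Counterpart in SPARCC |
|---|---|---|
| Joint margins and contour | 0-2 | None |
| Marrow signal | 0-3 | Sacroiliac oedema, if the item grades oedema |
| (no spinal item) | – | The spinal SPARCC has nothing to be compared with |

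The gap for the margin item is there whether the items are summed or analysed separately.

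**3. Illustrate the size.** Assumptions, none of them fixed by the documents:
- 66 abnormal and 66 normal dedicated scans. The number is borrowed for scale from the recruitment estimate in section 8.1, which concerns MRE-positive cases and matched controls.
- Every reading is correct.
- A scan is positive on the new score if either item is above 0 (no summing needed), and positive on SPARCC if above 0.
- A share f of the abnormal scans is structural-only: margin item above 0, SPARCC 0.

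SPARCC-negative scans = 66 + 66f. Of these, 66 are negative on the new score. Apparent specificity = 66 / (66 + 66f).

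| f | Structural-only scans | SPARCC-negative scans | Apparent specificity |
|---|---|---|---|
| 0% | 0 | 66 | 1.00 |
| 10% | 6.6 | 72.6 | 0.91 |
| 25% | 16.5 | 82.5 | 0.80 |
| 50% | 33 | 99 | 0.67 |

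All the loss comes from the criterion, since no reading is wrong.

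**4. Check whether the marrow item is safe.** Section 4.3.3 does not say that marrow signal means oedema only, and fatty or sclerotic change could also alter it. Let g be the share of structural-only scans with a marrow grade above 0. For the marrow item alone, apparent specificity = 1 − fg / (1 + f).

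| f | g = 0 | g = 0.5 | g = 1 |
|---|---|---|---|
| 10% | 1.00 | 1 − 0.05/1.10 = 0.95 | 1 − 0.10/1.10 = 0.91 |
| 25% | 1.00 | 1 − 0.125/1.25 = 0.90 | 1 − 0.25/1.25 = 0.80 |
| 50% | 1.00 | 1 − 0.25/1.50 = 0.83 | 1 − 0.50/1.50 = 0.67 |

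SPARCC is therefore a clean criterion for the marrow item only if that item is defined as oedema (g = 0).

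**The case against.** The strongest reply is that the plan never defines a total. It lists two sections with separate ranges, while it states totals for SPARCC explicitly, so a comparison item by item is compatible with the text. This stands, and it rules out an inference that a reader might draw: that 2 of 5 points, or 40% of the score, go unmeasured. That figure presupposes a sum that the documents do not make. The reply does not remove the concern, because an item-level analysis under the same rule would still hold the margin item to a criterion that cannot see it.

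A second reply is that nothing shows the score would be judged invalid. This also stands. With no statistic, threshold or share of structural-only scans, nobody can say that chronic sacroiliitis will make the score appear invalid.

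Third, the spinal SPARCC may never have been intended as comparator. The documents describe separate spinal and sacroiliac scores and do not say which is used, so this is a gap in wording and not an error.

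Fourth, much of the supportive evidence is already planned: 4.3.3 compares MRE with dedicated MRI scores, and 8.2 relates axSpA to MRE score. True, but not by item. Agreement between the two modalities also shows consistency, not that the item measures what it should.

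**Conclusion.** The concern holds in a limited form. As written, SPARCC cannot establish the validity of the margin item, and correctly read scans with margin change but no STIR signal would count against the new score. This follows from the scoring rules alone, given one inference: that joint margins and contour means structural change. The protocol does not use that word for the item, but its name and the chronic lesions in section 2.1 support the reading.

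The size is unknown. The apparent specificities of 0.91, 0.80 and 0.67 are illustrations that depend on the assumed shares of 10%, 25% and 50%, equal numbers of abnormal and normal scans, and a cut-off above 0.

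A reader might also infer that the study's main accuracy results are biased. The documents do not support that: sections 1.2 and 3.1 take dedicated axial MRI with clinical assessment as the reference, and nowhere equate it with SPARCC alone. The point concerns the validation of the score and the claim made from it. It is worth correcting because the correction is cheap.

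**What to change.** In sections 4.3.3 and 8.2:

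1. State that validation is by item, and name the statistic for each comparison in advance.
2. Compare the marrow-signal item with the sacroiliac SPARCC score only, not the spinal score.
3. State whether the marrow item grades oedema only or also fatty or sclerotic change. In the latter case, say that SPARCC covers only part of the item.
4. Do not use SPARCC as criterion for the margin item. Report for it the agreement between MRE and dedicated MRI on the same item, and its association with clinical axSpA. Label both as supportive evidence and not criterion validation, since the first shows only consistency and the dedicated MRI is itself part of the reference standard.
5. Limit any SPARCC-based validity claim to the marrow item.

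The cost is wording. The scores are already planned, so no further reading is needed. The downside is a narrower validity claim. A separate structural reading of the T1 images that 4.3.3 already acquires would be a stronger check on the margin item, but it would add reading time and is optional.

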1.2 Aim

The aim of this study is to determine the sensitivity and specificity of magnetic resonance enterography (MRE) as a screening tool for axial spondyloarthritis (axSpA) in a cohort of adult patients with Crohn's disease (CD) in a secondary-care hospital, using dedicated axial magnetic resonance imaging (MRI) with clinical assessment as the gold standard.

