1.5 Study group

The ProSpA-CD study will be divided into two parts:

ProSpA-CD-Screen Phase: Review of the patients MRE scan for evidence of axSpA

The gastroenterology team ([name]) at Cambridge University Hospitals (CUH) will write to approximately 1100 patients with a diagnosis of CD (male and female patients aged 18 years or above) who have had a MRE scan since 2015, asking for their consent to retrospectively review the MRE scans for evidence of axSpA. CD subjects with a known diagnosis of SpA (AS, axSpA, eSpA or

psoriatic arthritis) will be eligible and invited to enter the study. Subjects who consent to this will then have their MRE scans reviewed for this purpose.

ProSpA-CD-Assess Phase: Clinical assessment of case and control subjects for evidence of axSpA in the clinic setting

Patients with lesions on their MRE scan consistent with axSpA (regarded as 'cases'), but who do not have a known diagnosis of SpA, will be referred for further clinical assessment in the NHS rheumatology spondyloarthritis (SpA) clinic for evidence of axSpA ([name] NHS SpA clinic, but assessed by [name] in a supernumerary capacity). Patients will also be invited to participate in the ProSpA-CD-Assess phase of the study at this stage.

CD subjects with a known diagnosis of SpA who are already under review by rheumatology and who have lesions on MRE consistent with axSpA will be considered as cases but will instead be invited to attend the rheumatology SpA research clinic to be assessed for axSpA as this will be considered outside of their routine NHS care ([name] research clinic, but assessed by [name] in a supernumerary capacity).

CD subjects (including those with a known diagnosis of SpA) who had consented to have their MRE scans reviewed, but do not have evidence of axSpA on MRE will also be invited to participate in this phase of the study as 'control' subjects and consenting subjects will be referred for further clinical assessment in the rheumatology SpA research clinic for evidence of axSpA ([name] research clinic, but assessed by [name] in a supernumerary capacity). Cases and controls will be matched for sex and age, with a cases : control ratio of 1:1.

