4.3.2 Assessment of subjects with no lesions on MRE consistent with axSpA (controls)

Subjects (including those with a known diagnosis of SpA) who have consented to having their MRE scans reviewed, but who do not have lesions consistent with axSpA, will be informed in writing of this by the gastroenterology team. They will also be advised that they may be invited to enter the study as a control subject if they are randomly selected through matching (age and sex) to the enrolled 'MRE+ cases' (1:1 ratio). Matched potential control subjects will then be sent an invitation letter, PIS and reply slip (study interest form with a stamped-addressed envelope for returns) by the gastroenterology team to attend the rheumatology SpA research clinic to be assessed by [name] for clinical evidence of axSpA. CD subjects with a known diagnosis of SpA who are already under review by rheumatology and who have lesions on MRE consistent with axSpA will also be invited to attend this clinic for review outside of their routine NHS care but will be considered as cases. Informed consent for study participation in the SpA research clinic will be performed at the start of the consultation. The same clinical assessments, blood and stool samples and dedicated axial MRI scan of the spine and sacroiliac joints will be performed in this control group and in the group of CD subjects with a known diagnosis of SpA who are MRE+ as in the other cases, but will be funded by the research grant unless clinically indicated.

Control subjects in whom there is no evidence of axSpA (by ASAS, modified New York or CASPAR classification criteria) will be informed by letter, which will also be copied to the subjects GP and gastroenterology consultant. Control subjects who do have evidence of axSpA will be informed by letter (also copied to GP and gastroenterology consultant) and asked to return to [name] NHS rheumatology SpA clinic for ongoing care. CD subjects who already have a diagnosis of SpA (both in the control group and cases group) and are already under review by a rheumatology team will be informed by letter of the research clinic outcome and will be followed up as planned by their primary rheumatology team. We will also send a copy of the clinic letter to their GP, gastroenterology consultant and named rheumatology consultant to inform them of the clinic findings and to notify them of any outstanding tests/ management plans that may need to be considered at the next clinic review.

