5.2.2.1 Consent for retrospective review of the MRE scans (ProSpA-CD-Screen phase)

The gastroenterology team will write to all patients with CD and MRE scans since 2015 to ask for consent to review the images for evidence of axSpA. This correspondence will include a PIS and consent form with a stamped-addressed envelope for returns. The pack will also contain a BASDAI questionnaire with six simple questions relating to symptoms of axial inflammatory pain. These six questions, answered on a 1-10 VAS will pose low burden on the subject and be optional to complete, but will markedly help the research team gauge the impact of selection bias on the study given that there may be a preponderance of patients with axial pain willing to participate in the study.

5.2.2.2 Consent to enter the study as a case or control subject (ProSpA-CD-Assess phase)

Patients with lesions on MRE consistent with axSpA (and no known diagnosis of SpA) will be informed of this by the gastroenterology team (by telephone and letter) and be referred to [name] NHS SpA clinic for further clinical assessment. Once informed, they will also be invited by post to enter the research element of the study, with an invitation letter, accompanying PIS and reply slip (study interest form) with a stamped-addressed envelope to permit the patient to express if they do or do not wish to participate in the study.

CD subjects with a known diagnosis of SpA who are already under the care of a rheumatology team and have lesions on MRE consistent with axSpA will also be contacted by telephone and letter by the gastroenterology team. The subjects will then be sent a separate invitation letter, PIS and reply slip (study interest form) with a stamped-addressed envelope to permit the subject to express if they do or do not wish to participate further.

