Subjects (including those with a known diagnosis of SpA) without evidence of axSpA on MRE will be contacted by the gastroenterology team (by letter) to inform them of the results and will also be advised that they may be invited to enter the study as a control subject. Once the cases have been identified and enrolled, control subjects will then be randomly selected (age and sex-matched in a case : control ratio of 1:1) to enter the research element of the study. The gastroenterology team will then write to these subjects to invite them to enter the study, accompanied by a PIS and a reply slip (study interest form) with a stamped-addressed envelope to permit the subject to express if they do or do not wish to participate further. Any CD subjects with a history of SpA who have been selected as a potential control subject will be sent a separate invitation letter, PIS and reply slip (study interest form) by the gastroenterology team.

During the clinic consultation for both cases and controls, the research study will be discussed further and the subject will be provided with the opportunity to ask any questions they may have regarding the study. If the subject subsequently agrees to take part in the study, then inclusion and exclusion criteria will be assessed and informed written consent will be taken.

6. Study schedule

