8.1 Power analysis

This study will aim to include all CD cases with MRE imaging since 2015; the estimated sample size is therefore 1100 cases.

To our knowledge, there are no studies comparing the sensitivity and / or specificity of MRE scans with gold standard dedicated MRI for the detection of sacroiliitis. However, there have been some studies comparing CT imaging with MRI and these found MRI to be up to 17% more sensitive for the detection of sacroiliitis than CT [48, 49].

Although MRE is expected to be more sensitive at detecting evidence of sacroiliitis than CT, our power calculation is based on the conservative estimate that MRE will detect at $\geq 60\%$ (sensitivity) of

the cases of sacroiliitis, when compared with the gold standard dedicated axial MRI scan. Therefore with 80% power and a two-tailed alpha of 0.05, it is estimated that ≥ 60 control subjects (MRE normal) will be required for the study. It is estimated that a sample of >60 cases (with abnormal MRE scans) would be needed since the sample size required to assess specificity for a screening test is less than that of sensitivity. Case and controls will be recruited in a ratio of 1:1. From the 1100 MRE scans already performed, it is expected that $\geq 90\%$ will have a diagnosis of CD, i.e. 990 subjects. We estimate that $\geq 50\%$ of postally invited participants will consent to participate in the study, giving approximately 445 MRE scans for review.

The two previous studies assessing IBD patients for evidence of sacroiliitis using MRE imaging estimated the prevalence to be 16.7% and 15% [27, 28]. We therefore estimate to recruit ≥ 66 subjects with positive MRE scans (cases) and ≥ 66 matched controls. This is a conservative estimate, greater than the minimum number needed to recruit.

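### Sensitivity, specificity and AUC of MRE have no stated estimator or correction, although the reference MRI goes to MRE-positive enrollees and only an equal number of matched MRE-negative subjects; tabulated directly, a true sensitivity of 60% would read about 88–90%

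*Combined protocol and SAP*

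**What the plan says.** - **Aim.** Section 1.2: "The aim of this study is to determine the sensitivity and specificity of magnetic resonance enterography (MRE) as a screening tool", with dedicated axial MRI plus clinical assessment as the reference. Section 3.1 repeats this, and objective 1 (sections 1.3 and 3.2) adds AUC.
- **Who is verified.** Cases are MRE-positive subjects and controls are MRE-negative subjects. Section 1.5: "Cases and controls will be matched for sex and age, with a cases : control ratio of 1:1". Sections 4.3.2 and 5.2.2.2 draw the controls at random, within the match, from screened MRE-negative subjects once cases are enrolled. Section 4.3.3 says the dedicated MRI "will be performed in both the cases and controls"; unselected MRE-negative subjects do not receive it.
- **Analysis.** Section 4.3.3 says only "The sensitivity, specificity and area under the ROC curve of using MRE as a screening tool will also be determined". Section 8.2 lists intra-class correlations, the percentage of MRE-positive subjects meeting criteria, descriptive summaries and zero-inflated regression for association. It gives no estimator, weight or interval for the accuracy measures.
- **Sizing.** Section 8.1 assumes sensitivity of at least 60% for sacroiliitis against dedicated MRI, and concludes that at least 60 "control subjects (MRE normal) will be required for the study". It expects about 445 scans, and at least 66 MRE-positive subjects with at least 66 matched controls.
- **Selection bias.** Section 8.2 says volunteer bias rules out a prevalence estimate. Section 5.2.2.1 collects an optional BASDAI that "will markedly help the research team gauge the impact of selection bias on the study".

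**The concern.** Because case and control status is the MRE result, the 1:1 ratio fixes the MRE-positive share of the verified sample at one half, against roughly 15% of those screened. False negatives can only be found among MRE-negative subjects, and about five in six of these are never verified. A table built from the verified sample therefore understates false negatives relative to true positives, and true negatives relative to false positives. Sensitivity is pushed up and specificity down.

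What is at stake is the main result of a screening study. At the plan's 60% floor, a direct table would suggest that MRE misses about 1 in 10 patients with the target condition when it misses 4 in 10. The plan's remarks on selection bias concern willingness to take part, not verification that depends on the MRE result.

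**Working it through.** **Inputs from section 8.1:** about 445 scans; MRE-positive share q of 15% or 16.7%; at least 66 + 66 verified; 1:1 ratio; sensitivity Se of at least 0.60. **Assumption:** the documents give no PPV or axSpA prevalence, so PPV is set at 0.6 with a range of 0.4 to 0.8. PPV is needed for specificity, AUC, coverage and precision, but not for the bias in sensitivity.

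**1. The plan's figures.** 445 × 0.15 = 66.75, which reproduces the 66. (50% of 990 is 495, not 445; at 495 scans and 15% the factor in step 2 is still 5.7.) The requirement of 60 controls cannot be reproduced, because no null value or precision target is stated. A one-sample test of 0.60 at 80% power needs 194 against 0.50, 59 against 0.42 and 48 against 0.40.

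**2. Inflation factor.** With 1:1 sampling, an MRE-negative subject is verified f = q/(1−q) times as often as an MRE-positive one. Lower uptake among cases cancels, provided the 1:1 match holds and uptake is unrelated to disease.
- q = 15%: f = 0.176, so the TP:FN odds are inflated 1/f = 5.67 times.
- q = 16.7%: f = 0.200, inflation 4.99 times.
- 66 of 445: 379/66 = 5.74 times.

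**3. Apparent sensitivity = Se / [Se + (1−Se)f].**
- q = 15%: 0.60/(0.60 + 0.40 × 0.176) = 89.5%.
- q = 16.7%: 0.60/(0.60 + 0.40 × 0.200) = 88.2%.

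| True sensitivity | Apparent, q = 16.7% | Apparent, q = 15% |
|---|---|---|
| 40% | 76.9% | 79.1% |
| 60% | 88.2% | 89.5% |
| 80% | 95.2% | 95.8% |

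If the disease rate in matched controls were half or double that of all MRE-negative subjects, the 60% would read about 94% or 79–81%.

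**4. Specificity.** Let FOR be the disease rate among MRE-negative subjects: FOR = q·PPV·(1−Se)/[Se(1−q)]. With q = 66/445 = 0.148, Se = 0.6 and PPV = 0.6, FOR = 0.070 and true specificity is 0.930. Apparent specificity = (1−FOR)/[(1−FOR) + (1−PPV)] = 0.930/(0.930 + 0.400) = 0.699. At PPV 0.4, true 90% reads 61%; at PPV 0.8, true 96% reads 82%.

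**5. AUC, direction only.** Using (Se + Sp)/2 for a single cut-off at PPV 0.6, 0.765 becomes 0.798 when Se = 0.6, and 0.867 becomes 0.834 when Se = 0.8. The plan scores two ordinal scales, so these are not predictions.

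**6. Weighting restores the value.** At 66 + 66 with Se and PPV both 0.6, expect 39.6 true positives and 4.6 false negatives. Raw: 39.6/44.2 = 0.896. With MRE-negative subjects weighted by 5.74: 39.6/(39.6 + 26.4) = 0.60.

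**7. Interval coverage (simulation).** A 95% Wilson interval on the raw table contains the true sensitivity as follows:

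| Verified | Se | PPV | Coverage |
|---|---|---|---|
| 66 + 66 | 0.6 | 0.6 | about 0.1% |
| 46 + 46 | 0.6 | 0.6 | about 1% |
| 33 + 33 | 0.6 | 0.6 | about 7% |
| 66 + 66 | 0.8 | 0.6 | about 12% |

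**8. Precision after correction (simulation).** At Se and PPV both 0.6, with q held fixed, 95% of corrected estimates fall between 42% and 88% at 66 + 66, and between 37% and 100% at 33 + 33. Letting q vary over 445 scans widens the first range to about 41–88%.

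**The case against.** **The plan nowhere prescribes an unweighted table.** This is right. A reader might infer from section 8.1, which sizes the two groups without mentioning sampling fractions, that direct tabulation is intended. But sizing groups says nothing about how they will be weighted, and the documents do not settle it. The defect is an unspecified estimator for the main aim, and the bias is conditional. It is still more than missing detail: nothing in section 8.2 would prevent the direct table, and that table gives a wrong answer under this design.

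**Selection bias is already recognised.** In part. The BASDAI in section 5.2.2.1 is meant to gauge bias on the study as a whole, not only on prevalence. It addresses who volunteers, and does not repair verification that depends on the MRE result.

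**The 60% is not an axSpA figure.** Correct. Section 8.1 states it for sacroiliitis against dedicated MRI, as a conservative minimum. A reader might take the example as a forecast that MRE misses 4 in 10 patients with axSpA; the documents do not support that. At a true 80% the distortion is 15 to 16 points rather than 28 to 30.

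**PPV is safe.** Only in a limited sense. The 1:1 sampling does not itself bias PPV, but a reader should not infer that the share of new referrals without disease would be estimated correctly. Entry to the Assess phase is voluntary: if subjects with disease accept twice as often, a PPV of 0.60 is observed as 0.75. MRE-positive subjects with known SpA also count as cases (section 1.5) without being new referrals.

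**The corrected estimate is too imprecise to be useful.** The imprecision is real. It reflects what about five expected false negatives among 66 controls can tell us; a narrow interval around a biased value is no improvement.

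**Conclusion.** The point stands as an omission that must be repaired before the accuracy results are analysed. Verification depends on the MRE result, and the plan states neither an estimator nor a correction for its primary measures.

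If the 1:1 sample is tabulated directly, sensitivity is overstated by about 28 to 30 points at a true 60%, 37 to 39 at 40% and 15 to 16 at 80%. These figures rest on the plan's 15–16.7% MRE-positive share, on matched controls resembling all MRE-negative subjects, and on uptake unrelated to disease. Specificity is understated by an amount that depends on the assumed PPV (true 90–96% reads 61–82% over PPV 0.4 to 0.8). The direction of the AUC bias is not fixed.

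Coverage of a raw interval would be poor throughout the scenarios examined, but the near-zero figure belongs to 66 + 66 with sensitivity and PPV both 0.6 and should not be read as general.

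**What to change.** **Section 8.2**
- Make verification-corrected sensitivity, specificity and AUC the primary accuracy estimates (Begg-Greenes or inverse-probability weighting). Weight by number screened over number verified, within MRE result and coarse age-by-sex strata, with a pre-stated rule for collapsing sparse strata.
- Use confidence intervals that reflect the two-phase sampling and remain valid with few or no false negatives. The particular method is the trial statistician's choice.
- State the assumption that acceptance of the Assess phase is unrelated to disease within strata. Add a sensitivity analysis that brings the screening BASDAI into the weights where it was completed.
- Do not present unweighted two-by-two sensitivity or specificity as screening accuracy. If PPV is reported, separate known-SpA cases from new referrals.

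**Section 8.1**
- Replace the rationale for at least 60 controls with the expected precision of the corrected sensitivity at realistic uptake.

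**Cost.** SAP wording and modest programming. No extra scans are needed: every consenter's MRE is scored in the Screen phase, and age and sex are needed for the matching anyway. The reported estimate will be less precise and may look less favourable. Weighting does not remove acceptance bias: if subjects with disease accept twice as often in both groups, a true 60% would be estimated at about 50% (PPV 0.6). Verifying more MRE-negative subjects would narrow the range (66 + 150: about 47–77% with q fixed), but that is a separate design and budget decision.
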